1.2. Primary Safety Objective

Primary Safety Objective:

To evaluate the safety of treatment with EIDD-2801 in participants diagnosed with COVID-19

Primary Safety Endpoints:

- 1. Adverse events (AEs)
- 2. Serious adverse events (SAE)
- 3. Physical examination including vital signs
- 4. Safety laboratory assessments:
 - complete blood counts (CBC) with differentials
 - decrease in hemoglobin (Hgb) by >1 g/dL, or to <9 g/dL
 - decrease in platelet count by $50,000/\mu$ L, or to $<75,000/\mu$ L
 - comprehensive metabolic panels (CMP) including liver function tests
 - increase in aspartate aminotransferase (AST), alanine aminotransferase (ALT), amylase, or lipase to ≥3x the upper limit of normal (ULN)
 - urinalysis
- 5. Electrocardiograms (ECGs)

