The orally bioavailable isopropylester compound, EIDD-2801, has been evaluated in an ongoing, Phase 1, randomized, double-blind, placebo-controlled single-ascending and multiple-ascending dose first inhuman study to assess its safety, tolerability, and PK. A total of 130 healthy participants (109 males and 21 females) received at least 1 dose of EIDD-2801 or placebo in the Phase 1 trial EIDD-2801-1001. Preliminary, unblinded safety data are available for all subjects. Review of these safety data indicates that single oral doses of up to 1600 mg EIDD-2801 or placebo and multiple oral doses of up to 800 mg EIDD-2801 or placebo Q12H for 5.5 days have been generally well tolerated in healthy participants. Further details are provided in Section 2.3.1.

The prodrug (EIDD-2801) was generally not detectable in plasma following single (50 to 1600 mg) or multiple doses (50 to 800 mg BID for 5.5 days) of MK-4482. Plasma concentrations of the nucleoside metabolite (EIDD-1931) were detectable. T_{max} occurred approximately 1 hour post dose. Plasma EIDD-1931 concentrations generally declined in a monophasic manner, with a $t_{1/2}$ of approximately 1 hour. A biphasic profile with a later, slower elimination phase (t_{1/2} ranging from 1.47 to 19.2 hours) was observed in some participants (following single doses of 1200 mg and 1600 mg and following multiple doses of 600 mg and 800 mg). C_{max} and AUC increased in an approximately dose-proportional manner across the range of doses tested. No accumulation occurred following multiple dosing (Q12H for 5.5 days), and administration in the fed state did not meaningfully impact plasma exposure of EIDD-1931. There were no significant detectable concentrations of EIDD-2801; initial PK parameters were identified for EIDD-1931 concentrations in plasma. Following multiple doses of 100 mg BID EIDD-2801 orally in the fasted state, median t_{max} was 1.25 hours post-dose (range 1-2 hours), and concentrations declined monophasically and were quantifiable until the 6 to 9-hour time points. The apparent terminal half-life (t_{1/2}) was 0.918 and 0.969 hours on Days 1 and 6, respectively. AUC_{tau} was 853 ng*h/mL (%CV 19.9), and C_{max} was 395 ng/mL (%CV 18.5). The increase in exposure between the 50 mg and 100 mg doses was slightly supraproportional with the 2-fold increase in dose resulting in a 2.23-fold increase in AUCtau and 2.31-fold increase in Cmax. (EIDD-2801 Investigator's Brochure, V3.0, 2020).

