4.3. Intervention

4.3.1. Screening

Adult patients who are newly hospitalized with PCR-confirmed SARS-CoV-2 and evidence of symptomatic COVID-19 will be invited to participate in the study. Those who express interest will undergo the informed consent process and be given the chance to ask any questions before agreeing to participate. Those who consent to participate will undergo screening for study entry; the time between screening and study entry should be as short as possible (ideally the same day, but no longer than 48 hours). Screening assessments will include demographics, medical history, concomitant medications, review of inclusion and exclusion criteria, height, weight, BMI, physical examination including vital signs, clinical chemistry labs (CMP), hematology (CBC with differential), high sensitivity serum betahuman chorionic gonadotropin (HCG) (to rule out pregnancy) as applicable, urinalysis, electrocardiogram (ECG), and pulse oximetry. It is expected that measurements/values will have been obtained as SOC, and medical chart extraction will be performed. Missing values will be obtained as part of study procedures. Any chest radiography results from hospital admission will be recorded.

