During in-clinic study visits, partial pressure of oxygen (PO2) will be measured by oximetry, and oral temperature will be documented. Other vital signs will be assessed, and a targeted physical examination will be conducted as needed. AEs and concomitant medications will be collected that have occurred since the last visit/report. Safety lab assessment (CBC with differential, CMP, and urinalysis) will be conducted, and for women of childbearing potential, a high sensitivity serum pregnancy test will be performed at the end-of-study (EOS) visit or at early discontinuation. Results of a single post-dose ECG should be recorded. If the participant is discharged from the hospital before a post-dose ECG is recorded, and recording of an outpatient ECG is not feasible, then results of the last recorded ECG before hospital discharged will be entered into the CRF. The results of any chest diagnostics done as part of SOC will be recorded. Any SAEs will be followed for 30 days after the end of study participation as detailed in Section 8.10.3.

Participants who are discharged from the hospital before the EOS visit will continue to take study drug at home for the full 5 day course, and drug accountability will be conducted at the Day 5 and/or Day 8 interim study visits, where allowed by the study institution. Participants will be instructed on how to report worsening of disease, including development of any additional symptoms of pneumonia or other concerning illness that may require interim assessment including clinic or urgent visits.

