- k. Oxygen saturation is to be recorded twice daily (morning and evening) and may be ascertained by chart extraction; if not available in the participant's chart, it should be measured by the study staff.
- 1. Targeted physical examinations should be done if indicated by an AE or as needed in the judgement of the investigator.
- m. Laboratory measurements will include CBC with differentials, CMP (including amylase and lipase), and urinalysis.
- n. For ECGs, a single post-dosing recording should be collected. If the participant is discharged from the hospital before a post-dose ECG is recorded, and recording of an outpatient ECG is not feasible, then results of the last recorded ECG before hospital discharge will be entered into the CRF.
- o. Results of all chest radiography performed as part of routine clinical care during Study Days 1-28 should be recorded.
- p. Plasma and PBMC samples for PK analysis will be collected from participants if they are still inpatients on Day 3. Samples will be collected before the morning dose on Day 3 and at the following times after the Day 3 morning dose: 0.5 hours, 1.5 hours, 3 hours, 6 hours, 8 hours, and 24 hours (i.e., on the morning of Day 4). If a participant is scheduled to be discharged, then PK samples should be collected at all scheduled time points up to the time of discharge; in addition, if a participants is discharged prior to the 24-hour PK sample, a 12-hour PK sample should be collected, when possible. PK measurements will be assessed in participants enrolled at clinical sites able to conduct the collections. These sites include, but are not limited to,
 - be collected within a \pm 15 minute window (up to 3 hours), \pm 30 minutes (6-8 hours), or \pm 1 hour (12-24 hours).

	Outpatient ^a						
Study Procedures	Day 3	Day 5 ^b	Day 8 (±1 day)	Day 11 (±1 day)	Day 15 (±1 day)	Day 28 (EOS) (±2 days)	Early Discontin- uation
Serology (plasma) ^c		X				X	X
Pregnancy test ^d						X	X
Study residency							
Outpatient visit	X	X	X	X		X	X
Phone call ^e					X		
Study drug vs. placebo							
EIDD-2801 or PBO administration ^f	BID on Days 1-5	BID on Days 1-5					
Virologic endpoints							
NP swabs ^{g, h}	X	X	X	X		X	X
Clinical endpoints							
WHO Ordinal Scale (Appendix 1) ^h	X	X	X	X	X	X	X
Safety and tolerability							
Concomitant medication review	X	X	X	X	X	X	X
AE/SAE reporting h	X	X	X	X	X	X	X
Vital signs (temperature, blood pressure, pulse, respiratory rate) h	X	X	X	X		X	X
Pulse oximetry ^j	X	X	X	X		X	X

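### If post-dose means after the first dose, the ECG fallback can only enter a pre-dose tracing, which pulls a primary safety endpoint towards no change

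*Protocol*

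**What the plan says.** ECGs are the fifth primary safety endpoint in Protocol section 1.2. The pre-dose ECG is among the screening assessments in section 4.3.1: "urinalysis, electrocardiogram (ECG), and pulse oximetry".

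One later ECG is planned, and the protocol names it in three ways:

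- Section 4.3.4 calls it post-dose: "Results of a single post-dose ECG should be recorded".
- Footnote n of the inpatient schedule in section 7.1 calls it post-dosing: "For ECGs, a single post-dosing recording should be collected".
- The ECG row of that same schedule calls it posttreatment, to be done as feasible.

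The fallback stands in both section 4.3.4 and footnote n. Its trigger in 4.3.4 is: "If the participant is discharged from the hospital before a post-dose ECG is recorded, and recording of an outpatient ECG is not feasible". Its consequence is: "then results of the last recorded ECG before hospital discharged will be entered into the CRF".

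Three analysis statements bear on how the entry would be used. Section 6.2.2 analyses all data by nominal visit as set out in the schedule and eCRF, without visit windows. Section 6.2.7 summarises other safety data descriptively by dose group and scheduled time. Section 6.2.3 says missing safety data will in general not be imputed and leaves details and exceptions to the SAP.

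**The concern.** The rule is triggered by the absence of a post-dose ECG, yet it supplies a value from before discharge. If post-dose means after the first dose, any tracing that meets the rule was taken before study drug. Entered in place of the post-dose result, it compares baseline with baseline, or with another untreated tracing.

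The participants affected are not a random subset. They are people discharged early, some of them still taking study drug at home. Nothing in the protocol flags such an entry or keeps it out of the post-dose summary. A reader of the ECG tables could then take reassurance from tracings recorded with no drug given.

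**Working it through.** The protocol gives no figure for the ECG endpoint, so there is none to reproduce. The check is first one of wording, then an illustration of size.

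**Step 1: what the fallback can return under each reading**

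| Meaning of the later ECG | What is absent when the rule applies | What the last ECG before discharge can be |
|---|---|---|
| After the first dose | Any in-hospital ECG after the first dose | Only a pre-dose tracing. Normally the screening ECG, since no other pre-dose ECG is scheduled |
| After the end of treatment | An ECG after the last dose | The screening ECG, or a hospital tracing taken during treatment if routine care produced one |

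Under the first reading the entry is always pre-dose. Under the second it may be valid on-treatment information.

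**Step 2: does the entry reach the summary?** The screening ECG is collected anyway, so the rule has a purpose only if it fills the later ECG entry. Under sections 6.2.2 and 6.2.7 an entry made at a nominal visit is summarised at that visit. No text excludes it. In effect this is baseline carried forward, which sits badly with the general rule in section 6.2.3.

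**Step 3: size, by assumption.** Let f be the share of an arm whose screening ECG is entered as the later value. The protocol does not give f; 10% to 50% is assumed. Each of these participants has a recorded change of zero. If their true change would have been like that of the others:

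- observed mean change = (1 − f) × true mean change
- observed rate of new abnormality = (1 − f) × true rate

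For a rate example, assume a true rate of 20% and take 14 treated participants, the minimum expected in a higher-dose group in section 6.1. The chance of seeing at least one case is 1 − (1 − 0.20 × (1 − f))^14.

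| f | Share of true mean change observed | True 20% rate appears as | Chance of at least one case in 14 |
|---|---|---|---|
| 0% | 100% | 20% | 95.6% |
| 10% | 90% | 18% | 93.8% |
| 20% | 80% | 16% | 91.3% |
| 30% | 70% | 14% | 87.9% |
| 50% | 50% | 10% | 77.1% |

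**Step 4: unequal use between arms.** With the same true 20% rate and f of 40% in one arm and 20% in the other, the observed rates are 0.20 × 0.60 = 12% and 0.20 × 0.80 = 16%. That is a spurious difference of 4 percentage points. Within each arm the pull is still towards no change.

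**The case against.** **The reading is not settled.** Since the schedule row speaks of a posttreatment ECG and discharged participants go on dosing at home, the author may have meant an ECG after the course. Someone discharged during treatment has not had that ECG, and the last hospital tracing may well be on-treatment. Section 4.3.1 expects screening values to come largely from routine care, so ECGs outside the study schedule are plausible. This stands, and it limits the finding to a conditional one. It does not rescue the text, because sections 4.3.4 and 7.1 use terms that lead to opposite results.

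**It is a data-entry rule, not an analysis rule.** The text concerns the CRF, and the SAP, which is not at hand, could flag or exclude such entries. This also stands in part. Even so, the protocol asks for no date or time check that would make a pre-dose entry identifiable.

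**Materiality is not shown.** The rule needs two conditions, and clinic visits on Days 3, 5, 8, 11 and 28 give chances for an outpatient ECG. The endpoint has no named ECG variable or test, its analysis is descriptive, and section 2.3.1 reports no clinically significant ECG findings in Phase 1. All of this is correct and keeps the point modest.

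**A stronger reading to avoid.** From the half-life of about 1 hour in section 2.2, a reader might infer that the single later ECG is taken after the drug has washed out and so cannot show an effect. The documents do not support this. No passage places the ECG days after the last dose, and section 2.2 also reports a slower phase, with a half-life of up to 19.2 hours, in some participants.

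**Conclusion.** The point holds in conditional form. If post-dose means after the first dose, the fallback in section 4.3.4 and footnote n can supply only a pre-dose tracing, and it biases the ECG summary towards no change without any flag. If posttreatment is meant, the entry may be an on-treatment tracing and the bias is smaller. The protocol does not settle which is meant.

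The size is unknown. The retained 90% to 50% of a true mean change depends on three assumptions: f between 10% and 50%, the screening ECG being the tracing entered, and a true change in those participants similar to that in the rest. A reader might infer that the ECG endpoint is certainly biased, or biased by a stated amount. The documents support neither. Primary efficacy is not affected. The correction is worth making because this is a primary safety endpoint and the remedy is almost free.

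**What to change.** 1. Reconcile the three terms in section 4.3.4, the ECG row of the inpatient schedule and footnote n. Use one term and define it relative to the first and last dose.
2. Restrict the fallback, in both places, to ECGs recorded after the first dose.
3. Record the date and time of every ECG relative to the first and last dose, with a CRF check that a later ECG does not precede the first dose. An on-treatment tracing used under the fallback can then be identified as such.
4. Treat a pre-dose tracing as a missing post-dose ECG, in line with section 6.2.3.
5. Report by arm how many participants have a true post-dose ECG and how many are missing.

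The cost is amendment wording, a CRF field and an edit check. No additional ECG is required. The downside is that some participants will show as missing. If they differ from the rest, the summary of observed ECGs is still selective, but the gap is visible instead of being filled with an apparent absence of change.

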4.4. Pregnancy Testing

Pregnancy testing:

- Version: 7.0 18 May 2021
- Pregnancy testing requirements for study inclusion are described in Section 3.1.
- High sensitivity pregnancy testing should be conducted at screening (a serum test is required) within 24 hours of the first dose of study drug and on Day 28 approximately 23 days after the last dose of study intervention.
- Additional serum or urine pregnancy tests may be performed, as determined necessary by the investigator or required by local regulation, to establish the absence of pregnancy at any time during the subject's participation in the study.

4.5. Serology

Serology testing will be performed on plasma for IL-6 levels on Day 1 (pre-dose), Day 5, and Day 19. Samples will be archived for further cytokine testing in the future.

4.6. Rationale for Medication Dosing

Although 3 doses were effective in influenza models, the prolonged viral shedding that has been described in COVID-19 indicates that a longer dosing period may be beneficial. Also, allowing for differences between animal models and human disease, a margin of exposure at the top end of the range is desirable. Doses up to 800 mg twice daily are considered important to study in order to allow for sufficient exposure based on the use of data extrapolated from other species. Exploring a range of doses will allow for the selection of the best dose(s) to carry forward into subsequent studies.

Review of preliminary, unblinded data indicates that a treatment course of 5.5 days has been generally safe and well tolerated at multiple ascending doses (MAD) up to 800 mg, covering the doses planned for this efficacy/safety study. Also, single ascending doses (SAD) up to 1600 mg were similarly well tolerated, and PK has been dose-proportional in all cohorts. Refer to the IB for full information regarding animal efficacy studies and scaling to humans. Definition of an Overdose for this Protocol

For purposes of this protocol, an overdose is a single dose of more than 800 mg.

4.7. Concomitant Medications

Nucleos(t)ide analog drugs that are used for the treatment or prevention of HIV or hepatitis B virus are prohibited during the study, as are vaccines against COVID-19.

Remdesivir will be permitted. Corticosteroids for the treatment of COVID-19 will be permitted.

4.8. Study Discontinuation

If a participant is withdrawn from the study, the reason for withdrawal and the date the participant was removed will be documented in the case report form (CRF). A participant must be discontinued from the trial for any of the following reasons:

- Version: 7.0 18 May 2021
- The participant or legal representative (such as legal guardian) withdraws consent.
- Intercurrent illness that prevents further administration of treatment.
- Severe or life-threatening EIDD-2801-related AE(s).
- If in the opinion of the Investigator, a change or temporary or permanent discontinuation of therapy would be in the best interest of the participant.
- Noncompliance with trial treatment or procedure requirements.
- Participant is lost to follow-up.
- Participant becomes pregnant.

If a randomized participant withdraws from the study and has not been administered a dose of study drug or placebo, they will be replaced. Additional participants may be randomized, if needed, to ensure that an adequate number of participants provide Day 5 efficacy data.

Whenever possible, participants should continue to be monitored for safety through the remainder of the study.

The investigator should make every effort to perform the assessments indicated for the End-of-Study visit (see the Schedule of Events; Section 7.1) for participants who discontinue early from the study.

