4.3.2. Administration of Study Drugs

Upon completion of baseline assessments (including virologic assessments below), participants will then be administered the first dose of study drug (EIDD-2801 or placebo). Each participant will begin study treatment dosing with the first dose on the morning of Day 1, if possible. If the first dose is given later in the day, the second dose may be given at least 4 hours later on Day 1. Study drug administration will continue BID for a total of 5 days (10 doses). If the first dose on Day 1 is given in the late evening, the second dose may be taken on the morning of Day 2, in which case the final dose will be taken on the morning of Day 6.

In the event of missed doses, if the total number of missed doses is 4 or fewer, the number of days of study drug can be extended by no more than 1 day (through Day 6) with the equivalent of missed doses up to 2 doses. If the participant misses more than 4 consecutive doses, or more than 5 total doses, then the participant will be discontinued from any further study drug administration and followed for safety for the remainder of the study. Missed doses and times of administration will be recorded.

If a participant cannot ingest capsules orally during the study period, capsules will be opened, and the powder will be mixed with water and administered by mouth or through a nasogastric, percutaneous endoscopic gastrostomy (PEG) or orogastric tube.

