6.2.3. Handling of Dropouts, Missing Data, and Outliers

Participants who prematurely discontinue from the study without receiving a single dose of study drug or placebo will be replaced. Participants who receive at least a single dose of study drug who prematurely discontinue study drug should continue to undergo regularly scheduled visits, including an end of study visit at Day 28, to evaluate clinical assessments, AEs, and SAEs for the analysis of the primary efficacy endpoint, if there is no swab is available for analysis then the patient's response will be imputed to have a detectable level of SARS-CoV-2 RNA by qPCR (non-response). Longitudinal analyses of secondary endpoints, such as the rate of decline of log₁₀ viral RNA copies/mL for each method of sample collection, will use mixed effect models which are robust for missing data when this is missing completely at random (MCAR) or missing at random (MAR). Missing safety data will generally not be imputed. Details and exceptions will be provided in the SAP. No rules for outlier detection are planned.

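### Section 4.8 removes participants from the trial for treatment reasons, contrary to 4.3.2 and 6.2.3, and can selectively lose their Day 5 swab

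*Protocol*

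**What the plan says.** Protocol 4.8 (Study Discontinuation) opens its list with "A participant must be discontinued from the trial for any of the following reasons". Some entries are genuine exits from a trial, such as withdrawn consent and loss to follow-up. Others concern treatment: "Intercurrent illness that prevents further administration of treatment", a severe or life-threatening event related to the drug, an investigator's opinion that "a change or temporary or permanent discontinuation of therapy would be in the best interest of the participant", and "Noncompliance with trial treatment or procedure requirements". Section 4.1 describes a participant as enrolled until off study through discontinuation or completion, so discontinued is not a loose word here.

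Protocol 6.2.3 says: "Participants who receive at least a single dose of study drug who prematurely discontinue study drug should continue to undergo regularly scheduled visits", with an end-of-study visit at Day 28. Under 4.3.2, a participant who misses too many doses is "discontinued from any further study drug administration and followed for safety for the remainder of the study".

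For the primary endpoint, 6.2.3 says that where no swab is available the response "will be imputed to have a detectable level of SARS-CoV-2 RNA by qPCR (non-response").

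Section 4.8 softens its own rule in three ways. It asks for safety monitoring where possible, asks for every effort to perform the End-of-Study assessments, and allows extra randomization so that enough participants provide Day 5 efficacy data.

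**The concern.** Stopping a drug and leaving a trial are different events, and 4.8 merges them. If a site follows 4.8, a participant who may still be in hospital, consenting and able to be swabbed is taken off study before Day 5, and the primary outcome is lost for a reason linked to tolerability, intercurrent illness or adherence. Section 6.2.3 then replaces the missing result with a failure. If another site follows 6.2.3, the same participant contributes a real result. The primary comparison would then depend partly on which section each site reads.

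Non-response imputation is a legitimate rule. The defect is that 4.8 creates avoidable missing data for it to act on. The analysis plan cannot repair this later, because it cannot recover swabs that were never taken.

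**Working it through.** **Setting the passages side by side**

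- *Temporary stop of therapy.* Under 4.8 it leads to trial discontinuation. Section 4.3.2 tolerates missed doses and allows dosing to extend into Day 6.
- *Treatment noncompliance.* Under 4.8 it means leaving the trial. Under 4.3.2, missing more than 4 consecutive or more than 5 total doses means stopping drug with continued follow-up.
- *Does the softening text in 4.8 save the Day 5 swab?* Safety monitoring does not include swabs. In the inpatient schedule (7.1) the NP swab row is empty under both Day 28 and Early Discontinuation; the outpatient schedule marks both. Inclusion criterion 5 makes everyone an inpatient at first dose.
- *Would an early-discontinuation swab count as Day 5?* Section 6.2.2 uses nominal visits without windows, and nothing says that it would.
- *Which analysis set?* The Efficacy Analysis Set (6.2.1) needs at least one post-baseline qPCR result. Removal after the Day 3 swab but before Day 5 leads to imputation. Removal before any post-baseline swab leads to exclusion from that set, but to imputation in the intent-to-treat set. Section 6.2.4 does not name the set for the primary test.

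**Reproducing the plan's power**

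Inputs from 6.1: 14 per arm, 80% detectable on placebo and 20% on EIDD-2801, Fisher's exact test, α = 0.05 (taken as two-sided; the protocol does not say). Exact enumeration of two independent binomials gives 83.7%, matching the stated 83%.

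**Effect of imputed failures**

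The protocol gives no removal rate, so k = 1, 2, 3 of 14 is an assumption. With exactly k participants set to detectable, the expected detectable rate is

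- drug arm: [k + (14 − k) × 0.2] / 14 = 25.7%, 31.4%, 37.1%
- placebo arm: [k + (14 − k) × 0.8] / 14 = 81.4%, 82.9%, 84.3%

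| Set to failure | k = 0 | k = 1 | k = 2 | k = 3 |
|---|---|---|---|---|
| Drug arm only: power | 83.7% | 74.1% | 62.2% | 49.5% |
| k in each arm: power | 83.7% | 77.5% | 70.7% | 63.9% |
| Placebo arm only: power | 83.7% | 86.2% | 88.4% | 90.5% |

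The gain in the last row comes from failures assigned rather than observed.

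**How much of the loss the fix recovers**

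If removed drug-arm participants would have cleared at the planned drug rate, keeping their swabs restores 83.7%, a recovery of 9.6, 21.5 and 34.2 points. If they would instead have looked like placebo (80% detectable, an assumption), keeping every swab gives 76.5, 68.0 and 58.9%, and the recovery is 76.5 − 74.1 = 2.4, 68.0 − 62.2 = 5.8 and 58.9 − 49.5 = 9.4 points.

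**If the drug has no effect**

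With 20% removed from one arm only and imputed, the two-sided rejection rate moves from 1.6% to 1.8% when both arms are truly 80% detectable, and from 1.6% to 8.3% when both are truly 20% detectable.

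**The case against.** The strongest reply is that the harm is conditional, and much of that stands.

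- A reader might infer that everyone removed before Day 5 is counted as a virologic failure. The documents do not support that. Imputation applies only where no swab is available, the outpatient schedule has a swab at Early Discontinuation, and removal before any post-baseline swab means exclusion from the Efficacy Analysis Set. Exclusion costs little power (14 v 13 gives 86.2%), but it is selective too.
- Section 4.8 allows extra randomization for Day 5 data, and the Protocol Summary allows up to 15% above 84. This can offset lost power. It cannot replace the outcomes of those removed.
- Fourteen on placebo is a floor. With 21 pooled placebo participants (illustrative), power is 94.9% with none removed and 81.7% with two removed on drug.
- A reader might infer that the rule removes precisely those whose COVID-19 worsens. Worsening is not itself a listed reason. Those who cannot swallow capsules may be dosed by tube (4.3.2), and ventilated participants remain subject to virologic sampling (4.3.3). The noncompliance entry also covers procedures, and someone who refuses swabs has no Day 5 result under any wording.
- A reader might infer that the missing-at-random assumption fails. That is not shown: missingness may depend on treatment and on earlier observed viral loads without violating it. Removal for these reasons may strain the assumption, and no more can be said.
- Losses on drug work against EIDD-2801, so the imputation is conservative in that case. It is not conservative if placebo loses more.

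None of this removes the contradiction between 4.8 and the other two sections.

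**Conclusion.** The point holds as an internal contradiction with a consequence for the primary endpoint. Section 4.8 requires trial discontinuation for treatment reasons, whereas 4.3.2 and 6.2.3 stop drug and keep follow-up. Nothing in 4.8 secures the Day 5 swab. The resulting loss is selective and can bias the primary comparison, in a direction the documents do not determine.

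The size cannot be forecast without a removal rate. At 14 per arm a single drug-arm participant scored as a failure costs about 10 points of power, of which the fix might recover as little as 2 if that participant would have responded like placebo. These figures assume the planned 80% and 20% rates, a two-sided test and no top-up randomization. The change should be made: the risk is avoidable and the remedy is cheap.

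**What to change.** Reconcile 4.8 with 4.3.2 and 6.2.3:

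1. Separate discontinuation of study drug from withdrawal from the trial, and assign each listed reason to one or the other.
2. State that participants who stop study drug, but have not withdrawn consent or been lost to follow-up, keep all scheduled visits, including both NP swabs on Day 5.
3. Add the NP swab to the Early Discontinuation column of the inpatient schedule, as in the outpatient schedule.
4. State whether an early-discontinuation swab counts towards the Day 5 endpoint.

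When treatment is stopped, and how pregnancy and refusal of procedures are handled, remain for the sponsor to decide. The cost is wording, plus one swab collection for inpatients who leave early. The Day 5 visit and its swabs are already scheduled.
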